## 9.3 Additional Analyses

Number of patients that successfully received the intervention

Rate of appreciation for proactive phone communication from WLA Cardiology.

Rate of medication titrations per half day panel clinic vs. usual HF clinics for 10 clinics matched by week during the study period.

## 10 Safety Analysis

Clinicians involved with the intervention will report acute kidney injury (AKI) defined as 25% decrease in GFR from baseline on follow-up labs (1-week for MRA and 1-2 weeks for ACE/ARB/ARNI) after a successful medication titration within the intervention group. Laboratory alerts will be followed by pilot study clinicians. Hospitalization related to adverse medication event (e.g. symptomatic hypotension, AKI, hyperkalemia) related to the intervention. Difference in mortality between intervention and usual care.

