4.3 Randomization and Blinding

Patients will be randomized 1:1 to intervention and usual care groups with all patients randomized at one time; given the target sample size of n=300 total patients, the sequence will be generated using permuted blocks of size 6 to ensure that an equal number of patients are randomized to panel management and usual care, maximizing efficiency (power). The randomization sequence will be concealed from the clinicians until after randomization has already been complete. Post-randomization, study staff will not be blinded to allocation. GLA IRB exemption was granted for consent of the low risk, non-experimental intervention. The intervention does not allow for blinding of participants in the intervention arm.

Figure 1: CONSORT Study Flow Diagram Template

5 Safety

Clinicians involved with the intervention will report acute kidney injury (AKI) defined as 25% decrease in GFR from baseline on follow-up labs (1-week for MRA and 1-2 weeks for ACE/ARB/ARNI) after a successful medication titration within the intervention group. Laboratory alerts will be followed by pilot study clinicians. Hospitalization related to adverse medication event (e.g. symptomatic hypotension, AKI, hyperkalemia) related to the intervention. Difference in mortality between intervention and usual care.

6 Adverse Events

Specific adverse events of interest include symptomatic hypotension documented in the EHR. Hospitalizations related to heart failure will be captured during the study end using the ADHFD. If patients were removed from the dashboard at 6 months, a chart review will be performed to abstract missing data.

7 References

8 Listing of Tables, Listings, and Figures

Figure 1: CONSORT Study Flow Diagram Template

8

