## 5 Study Methods

### 5.1 General Study Design and Plan

This is a randomized, pragmatic QI study designed to evaluate the effectiveness of proactive panel management to close gaps in evidence-based care for patients with HFrEF. We will use the VA's ADHFD to generate a list of actionable patients with HFrEF and left ventricular ejection fraction (LVEF)  $\leq 35\%$ . After identifying a cohort of HFrEF patients from the ADHFD, we will randomize individual patients on the actionable list to usual VA care or a novel proactive panel management clinic. Clinicians will be trained on how to use the dashboard information to identify opportunities for optimization based on detailed chart review. The proactive panel management intervention will use clinicians to perform an electronic chart review and call patients impromptu at their discretion to evaluate HFrEF management and opportunities to optimize GDMT. Each panel management clinic is staffed by a single cardiovascular clinician or trainee with cardiology (PI) supervision. All patients will receive chart review or telehealth notes brought to the attention of primary care and cardiology clinicians. Patients randomized to the intervention will only receive one chart review during a half-day panel management clinic with follow-up of any laboratory results or diagnostic tests as required and referral to HF or general cardiology clinic as deemed appropriate. The control arm consists of the usual delivery of health services with routine scheduled appointments for primary care or cardiology.

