### **5.3 Randomization and Blinding**

Patients will be randomized 1:1 to intervention and usual care groups with all patients randomized at one time; given the target sample size of n=300 total patients, the sequence will be generated using permuted blocks of size 6 to ensure that an equal number of patients are randomized to panel management and usual care, maximizing efficiency (power). The randomization sequence will be concealed from the clinicians until after randomization has already been complete. Post-randomization, study staff will not be blinded to allocation. GLA IRB exemption was granted for consent of the low risk, non-experimental intervention. The intervention does not allow for blinding of participants in the intervention arm.

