### **7.2 Analysis Populations**

All subjects randomized per intention to treat. Any deaths, hospitalizations that occur prior to receipt of the intervention will be included in the primary analysis.

Secondary outcomes assessment will evaluate patients that received the telephone intervention vs. did not receive any protocolized interventions.

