## 9 Efficacy Analysis

The analysis will evaluate differences between usual care and the intervention arm (intention to treat) in the receipt of active prescriptions for GDMT, hospitalizations, and mortality.

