### 9.1 Primary Efficacy Analysis

The primary analysis will evaluate the effectiveness of the proactive panel management intervention compared to usual care using the OPS score 6-months after the last participant in the intervention arm receives the intervention. The difference in the OPS score between usual care and intervention will be estimated using a parametric ANCOVA with baseline OPS as a covariate as well as restricted cubic spline adjusting for baseline age. Age is specified as it may relate to the tolerance and probability of receiving more classes of medications.

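### AKI is planned as a one-arm count after titration in the intervention group, so it cannot be set against usual care

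*SAP*

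**What the plan says.** SAP section 10 states: "Clinicians involved with the intervention will report acute kidney injury (AKI) defined as 25% decrease in GFR from baseline on follow-up labs". The sentence goes on to give laboratory timings (1 week for MRA, 1 to 2 weeks for ACE/ARB/ARNI) and restricts the setting: "after a successful medication titration within the intervention group. Laboratory alerts will be followed by pilot study clinicians". Protocol section 5 repeats the restriction: "after a successful medication titration within the intervention group".

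Other parts of the plan that bear on this:

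- **Blinding.** SAP section 5.3: "Post-randomization, study staff will not be blinded to allocation".
- **Drug-related hospitalization.** The same safety paragraph lists admissions for adverse medication events, with AKI as an example, but words them as events attributable to the intervention. The only safety item there that is worded as a difference between arms is mortality.
- **What is compared by arm.** SAP section 9 covers "differences between usual care and the intervention arm (intention to treat) in the receipt of active prescriptions for GDMT, hospitalizations, and mortality". No renal outcome is listed.
- **Population and primary outcome.** SAP section 7.2: "All subjects randomized per intention to treat". SAP section 9.1 evaluates the intervention "using the OPS score 6-months after the last participant in the intervention arm receives the intervention".
- **How the intervention acts.** Besides direct titration by panel clinicians, SAP section 5.1 provides for chart-review notes to other clinicians, requests for later cardiology visits, and "referral to HF or general cardiology clinic as deemed appropriate".
- **Renal data on hand.** SAP section 5.4 includes creatinine and eGFR in the dashboard data, which are exported at baseline and at final evaluation. Table 2 carries an eGFR date and takes creatinine as the latest value within a year.

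**The concern.** The intervention is meant to raise use of ACE/ARB/ARNI and MRA, and the plan itself names AKI as a safety event of these changes. The benefit will be a randomized difference over all 300 patients, whoever wrote the prescription. The harm will be a count from one arm, made by unblinded staff, among patients who were titrated. Being titrated is decided after randomization, and usual care has no matching subgroup.

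Patients with an LVEF of 35% or less will have some AKI under any care. Without a usual-care figure, a reader cannot tell background events from added ones, or weigh AKI against the gain in OPS.

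**Working it through.** **1. Can the planned AKI result be compared?** The plan states no AKI figure to reproduce, so this step is a reading of the text.

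| Element | OPS | AKI |
|---|---|---|
| Arms | both | intervention only |
| Patients | all randomized | those with a successful titration |
| Source | dashboard export, chart review if missing | report by intervention clinicians |
| Contrast | difference between arms | none stated |

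The excess is the intervention rate minus the usual-care rate in comparable patients. The plan supplies neither the second term nor a comparable group. As an illustration with assumed rates, 10% AKI among titrated patients would mean an excess of 10, 5 or 0 points if the background were 0%, 5% or 10%. Nothing collected under the plan chooses among these. The number titrated is not given either, so no interval can be attached.

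**2. Precision with both arms measured.** Inputs: 300 patients at 1:1 (SAP section 5.3), so 150 per arm. AKI rates and SDs are assumptions.

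- AKI risk difference, half-width = 1.96 × √(2p(1−p)/150):
  - p = 5%: 4.9 points
  - p = 10%: 6.8 points
  - p = 20%: 9.1 points
- Difference in eGFR change, unadjusted half-width = 1.96 × SD × √(2/150):
  - SD 10: 2.3 mL/min
  - SD 15: 3.4 mL/min
  - SD 20: 4.5 mL/min
- The same if 80% versus 60% have a post-randomization value (120 versus 90, assumed), with √(1/120 + 1/90) in place of √(2/150): 2.7, 4.1 and 5.5 mL/min.

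**3. Would a two-arm AKI count measure excess AKI?** Let q be the chance that one laboratory result shows a 25% fall from background variation alone. A patient with k results is flagged with probability 1 − (1 − q)^k, taking results as independent. With 4 versus 2 results per patient (assumed) and no true effect:

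| q | Intervention | Usual care | Spurious difference |
|---|---|---|---|
| 2% | 7.8% | 4.0% | 3.8 points |
| 3% | 11.5% | 5.9% | 5.6 points |
| 5% | 18.5% | 9.8% | 8.8 points |

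In the last row the half-width is 1.96 × √((0.185 × 0.815 + 0.098 × 0.902)/150) = 7.8 points. A plain 95% interval would then exclude zero with no true effect. The two-arm count is worth reporting, but as description only.

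**4. Can a final dashboard value predate randomization?** The creatinine look-back is one year (52 weeks), and final evaluation is 6 months (26 weeks) after the last clinic. At 10 to 15 patients per clinic, 150 patients need 10 to 15 clinics. If these run weekly from randomization (assumed), final evaluation falls at 36 to 41 weeks. A final creatinine could then predate randomization by up to 52 − 41 = 11 to 52 − 36 = 16 weeks. Final values therefore need a date check.

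**The case against.** The best defence is that the AKI text describes clinical monitoring in a low-risk quality-improvement study of approved drugs. Where the authors wanted a between-arm safety contrast they wrote one, for mortality, and nothing promises an AKI comparison. It is right that the documents do not contradict themselves here. But the rule sits in the safety analysis section with a numerical definition, and followed exactly it produces an uninterpretable count for a harm the plan chose to name.

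A second objection is that the remedy has its own bias. This stands. Step 3 shows unequal testing alone can produce a difference as large as its interval. The eGFR comparison avoids inflation from repeated tests, but it depends on who was tested after randomization and shows persistent decline rather than transient AKI.

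Three stronger readings are tempting, and the documents do not support them:

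- **That AKI after titration by other clinicians is definitely missed.** The text limits reporting to titrations within the intervention group without saying whose, and SAP section 5.1 provides for follow-up of laboratory results as needed. Whether such events are captured is unclear.
- **That usual care has no renal data.** Creatinine and eGFR are in both exports. What is missing is an analysis that uses them.
- **That the 1 and 1-to-2-week timings are a reporting cutoff.** They match the laboratory schedule in Supplement S2 and can be read simply as when tests are drawn.

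**Conclusion.** The point holds in a limited form. As planned, AKI is a one-arm count by unblinded clinicians in a subgroup defined after randomization. It cannot be compared with usual care or set beside the randomized OPS difference. The drug-related hospitalization item is no substitute, because it too is worded around the intervention. All-cause admissions are counted as a secondary outcome, but AKI admissions are not separated out.

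A reader might infer that harm is being understated, or that the efficacy result is compromised. Neither follows. The size of any undercount cannot be derived from the documents, and the primary estimate is untouched. All AKI rates, SDs, test counts, testing shares and clinic frequencies used above are assumptions. This is a cheap improvement, of lower priority than points that affect the primary result.

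**What to change.** Keep clinician reporting and laboratory alerts for patient care. In SAP section 10 and Protocol section 5, add two items:

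1. **eGFR change by arm.** Compare baseline-to-final eGFR change between arms in all randomized patients, adjusted for baseline eGFR, from the two dashboard exports already planned. Use only final values dated after randomization, and report the share of patients with such a value in each arm.
2. **Descriptive AKI by arm.** Apply the 25% criterion in the same way to existing EHR creatinine/eGFR results in both arms, from randomization to final evaluation, whoever prescribed. Report patients tested, results per patient and patients meeting the criterion. State that this does not estimate excess AKI.

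**Cost.** Wording in both documents and a modest laboratory data pull or chart abstraction for 300 patients. The first item mainly uses data already due to be exported.

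**Downsides.** Intervals are wide (about 5 to 9 points for an AKI risk difference at assumed rates of 5% to 20%). More testing after titration will inflate detected AKI in the intervention arm. The eGFR comparison depends on who was tested after randomization and does not capture transient AKI.

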### 4.2.2 Secondary outcome

The secondary outcomes of the study will include the following at final evaluation:

1. Active prescriptions for individual classes of GDMT
  - a. ACE/ARB/ARNI
  - b. Beta-Blocker
  - c. MRA
  - d. ARNI
  - e. SGTL2i
2. Hospitalizations
  - a. Total number of any cause hospitalization
  - b. Total number of primary HF hospitalizations
  - c. Proportion of patients with any hospitalization
  - d. Proportion of patients with any HF hospitalization
3. Number of deaths
4. Clinician time spent per patient from opening chart to end of patient-specific intervention and documentation.
5. Health service efficiency
  - a. Number of patients reviewed or contacted per half-day clinic
  - b. Number of medication adjustments (stop, start, titration) per half-day clinic
  - c. Number of laboratory tests ordered per half-day clinic
  - d. Number of imaging/diagnostic procedures ordered per half-day clinic
  - e. Number of referrals for consults/device therapy per half-day clinic
6. Qualitative evaluation of patient surveys who received the intervention.

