### **5.4 Study Assessments**

Data for analysis will be pragmatically ascertained through the variables available in the ADHFD. The ADHFD data will be exported at baseline. To evaluate study outcomes, the ADHFD will be exported again to a secure Excel file 6-months after the last participant receives the intervention. The ADHFD data includes age, race, hospitalization risk scores, number of VA hospitalizations in the past 12 months, vital signs (weight, blood pressure, pulse), laboratory values (potassium, creatinine, BNP, eGFR), active GDMT prescriptions, and upcoming appointments. Sem-structured survey data will be captured by clinicians for only intervention patients. No interim analyses are planned. Longer term secondary evaluations will be evaluated at 1 and 2 year.

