### 10.1 Adverse Events

Specific adverse events of interest include symptomatic hypotension documented in the EHR. Hospitalizations related to heart failure will be captured during the study end using the ADHFD. If patients were removed from the dashboard at 6 months, a chart review will be performed to abstract missing data.

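### AKI, potassium and cause-specific medication hospitalization have no between-arm estimate; add a randomized laboratory comparison restricted to post-randomization values

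*SAP*

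**What the plan says.** SAP Section 10 and Protocol Section 5 carry the same safety text.

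- **AKI.** "Clinicians involved with the intervention will report acute kidney injury (AKI) defined as 25% decrease in GFR from baseline on follow-up labs", with windows of "1-week for MRA and 1-2 weeks for ACE/ARB/ARNI", and only "after a successful medication titration within the intervention group". No reporter, window or count is given for usual care.
- **Medication-event hospitalization.** "Hospitalization related to adverse medication event (e.g. symptomatic hypotension, AKI, hyperkalemia) related to the intervention". An event attributed to the intervention cannot occur in usual care.
- **Mortality.** "Difference in mortality between intervention and usual care". This is the only between-arm comparison inside Section 10.
- **Symptomatic hypotension.** SAP 10.1: "Specific adverse events of interest include symptomatic hypotension documented in the EHR". Neither an arm limit nor a comparison is stated.

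Elsewhere, SAP 4.2.2 lists "Total number of any cause hospitalization" and deaths as secondary outcomes, and the opening of SAP Section 9 commits to evaluating hospitalizations and mortality between arms by intention to treat. SAP 5.4 exports the dashboard at baseline and again six months after the last participant receives the intervention. The export includes "laboratory values (potassium, creatinine, BNP, eGFR" and is not limited to one arm; the only item 5.4 confines to intervention patients is the survey.

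**The concern.** The intervention is meant to increase prescribing of RAAS inhibitors, MRAs and SGLT2 inhibitors, and Section 10 itself names AKI and hyperkalemia among the events to watch. Yet AKI is counted in a subgroup formed after randomization (patients who were titrated), by clinicians who know the assignment, and with no comparator. Some of these patients would show a 25% fall in GFR whatever the trial did. A one-arm count cannot separate that background from harm, so it could wrongly incriminate the intervention or falsely reassure. The trial could report better prescribing with no randomized estimate of its renal or potassium consequences, although laboratory values for both arms are already being exported.

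**Working it through.** **1. Where each item is counted and compared**

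| Item | Place | Arms counted | Between-arm analysis |
|---|---|---|---|
| AKI | SAP 10, Protocol 5 | Intervention, after titration | None |
| Medication-event hospitalization | SAP 10, Protocol 5 | Intervention, by attribution | None |
| Potassium | SAP 5.4 export; hyperkalemia is only an example cause in SAP 10 | No limit on the export | None |
| Symptomatic hypotension | SAP 10.1, Protocol 6 | No limit stated | None stated |
| Mortality | SAP 4.2.2, 9, 10 | Both | Difference |
| Any-cause hospitalization | SAP 4.2.2, 9 | Both | Promised in Section 9; no method named in 9.2 |

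The first three rows are the gap.

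**2. The plan's own figure.** No rate or precision is stated for any safety event. The only design figure is 83% power for the primary score (SAP Section 6). With a difference of 0.25 × 2.4 = 0.6, SDs 1.5 and 1.9, 150 per arm and an assumed two-sided 5% level: SE = √((1.5² + 1.9²)/150) = 0.198, 0.6/0.198 = 3.04, and power = Φ(3.04 − 1.96) ≈ 86%. The stated figure is slightly conservative and has no bearing on this point.

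**3. What a one-arm count would show with no harm.** Arm size is 300/2 = 150. The number titrated is not given, so 150 is the ceiling. The background rate is not given either, so 2% to 20% is assumed. Expected events are at most 150 × p: 3 at 2%, 7.5 at 5%, 15 at 10%, 30 at 20%.

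**4. Precision if both arms are assessed alike.** Half-width = 1.96 × √(p₀(1−p₀)/n + p₁(1−p₁)/n). All rates are assumptions.

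- 5% vs 10%, n = 150: 1.96 × √(0.0475/150 + 0.0900/150) = 1.96 × 0.0303 = 5.9 points.
- 10% vs 15%, n = 150: 1.96 × √(0.0900/150 + 0.1275/150) = 1.96 × 0.0381 = 7.5 points.
- Equal rates of 2%, 5%, 10%, 20%, n = 150: 3.2, 4.9, 6.8, 9.1 points.
- If only 100 per arm had usable labs (assumed): 1.96 × √(0.1375/100) = 7.3 points for 5% vs 10%, and 1.96 × √(0.2175/100) = 9.1 points for 10% vs 15%.

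**5. What the exported values can and cannot do.** SAP Table 2 gives potassium and creatinine as the latest value within the preceding year; eGFR has a date but no stated look-back. If clinics run for c months after randomization, the final export falls about c + 6 months after randomization. The 12-month look-back then reaches 12 − (c + 6) = 6 − c months before randomization. With c under six months, a patient with no new test can carry a pre-randomization value into the final export, and if it is the baseline value itself the change is exactly zero. Titration triggers labs in the intervention arm (SAP 5.1 and Supplement S2), so such stale values would collect mainly in usual care and would look present rather than missing. Table 2 includes the lab dates, so they can be identified. Two snapshots still cannot reproduce AKI at one to two weeks, and the export does not record why a patient was hospitalized.

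**The case against.** The strongest reply is that the AKI item is clinical follow-up of study-ordered labs in an intervention that SAP 5.3 calls low risk. A listing suits that purpose, and the plan never presents it as a comparative estimate. That stands for the listing; it does not supply the missing comparison.

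A reader might infer that mortality is the only harm compared between arms. The documents do not support this. An admission for AKI, hyperkalemia or hypotension falls within any-cause hospitalization, which Section 9 commits to comparing. It is a partial answer: the total mixes benefit with harm, fewer heart failure admissions could mask more renal or potassium events, and the only hospitalization method named in 9.2 is a hazard ratio for heart failure hospitalization.

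A reader might also infer that both restricted events are counted only after titration. That wording applies to AKI alone; hospitalizations are restricted by attribution. Nor is symptomatic hypotension confined to one arm by the text.

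Finally, a laboratory comparison would be imprecise: both half-widths for a five-point difference exceed five points, even with complete data, and the assumed rates have no source in the documents. That is correct. It is a reason to report an estimate with its interval and not to rest on a test.

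**Conclusion.** The point holds in limited form. As written, the plan gives no between-arm estimate for AKI, potassium or cause-specific medication hospitalization. It does compare mortality and any-cause hospitalization, so it would be wrong to say that the trial has no randomized information on harm. It would also be wrong to say that the existing export yields a comparison of early AKI: it supports only a final-evaluation comparison, and only after undated or pre-randomization values are set aside.

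That comparison would have a 95% CI half-width of about 6 to 7.5 points, assuming rates of 5% to 15%, 150 per arm and complete labs, and wider with missing values. The change should be made, but the primary analysis does not depend on it.

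**What to change.** Amend SAP Section 10, and align Protocol Section 5, as follows.

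- Compare by assigned arm, in all randomized patients with usable values, the proportion with an eGFR fall of at least 25% and the mean change in eGFR and potassium from baseline to final evaluation, using dashboard values.
- Count a final value only if its lab date (Table 2) is after randomization. Report the number with such a value by arm, and each difference with a 95% CI.
- Add these labs to the chart abstraction for patients who have left the dashboard. SAP 7.4 promises abstraction only for data needed in the primary or secondary analyses.
- Keep the clinician-reported early AKI count as a descriptive intervention-arm listing, and draw no comparative conclusion from it.
- State that any-cause hospitalization, compared between arms with a named method and a CI, is the randomized measure of serious harm. Classifying medication-related hospitalizations by one rule in both arms is optional.

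**Cost.** SAP wording, one table from exported fields, and some added chart abstraction; no change to care. The optional classification needs extra chart review in both arms.

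**Downside.** Lab timing and completeness will differ by arm, so the comparison among patients with values is not fully protected by randomization. Early transient AKI is not captured, and precision is modest.
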